#### **6.5 Blinding**

##### **6.5.1 Method of Blinding**

This is an open label study.

##### **6.5.2 Unblinding**

This is an open label study; therefore, there is no unblinding involved.

#### **6.6 Prior and Concomitant Therapy**

Chronic medications being used at the time of the Screening and Baseline Visit, with the exception of those specified as prohibited, may be continued at the discretion of the Investigator. History of medications, therapies and procedures are collected from the prior 2 month period for determination of eligibility.

---

New medications or the change in a dose of a current medication, required for another medical condition, which in the opinion of the investigator will have no material impact on the study, are permitted. The addition of such a new medication during the study will be documented as a concomitant medication and the associated medical need must be recorded as an adverse event.

All medications (topical, oral, prescription, over-the-counter, and herbal medications) and medical therapies or procedures that are used during the study for other diseases/conditions must be recorded on the CRF. Medications taken before the Baseline Visit need not be recorded on the CRF but should be reviewed to determine eligibility.

The following medications are prohibited during the study:

- inhaled, intraocular, intranasal steroids, etc
- systemic steroids
- systemic antipsoriatics (methotrexate, cyclosporine, hydroxyurea)
- PUVA therapy
- UVB therapy
- topical antipsoriatic drugs (salicylic acid, anthralin, coal tar, calcipotriene)
- topical corticosteroids
- immunosuppressive drugs (tacrolimus, pimecrolimus)
- topical retinoids (azarotene, tretinoin)
- systemic anti-inflammatory drugs (mycophenolate mofetil, sulfasalazine, 6-thioguanine)
- biologics (infliximab, adalimumab, etanercept, ustekinumab, secukinumab or alefacept)
- oral retinoids (acitretin, isotretinoin)

The use of illegal drugs or prescription drugs that have not been prescribed for the subject are not permitted during the study.

Topical products other than the assigned treatment including moisturizers, creams, ointments, lotions, and powders applied on or near the affected areas that are being treated with study product should not be used during the study from Baseline Visit to End of Treatment Visit. Moisturizers can be used on the face, scalp, groin, axillae and other intertriginous areas. If a subject has been regularly using an anti-psoriasis, medicated shampoo product (e.g., tar shampoo, salicylic acid shampoo, zinc pyrithione) on the scalp for 3 months prior to randomization, he/she may continue on the same. Subjects with scalp psoriasis may not start the use or change the use of an anti-psoriasis, medicated shampoo product for the scalp during the study.

Use of the following should not occur during the study:

- tanning booths, sun lamps, or nonprescription UV light sources
- phototherapy
- sunbathing
- occlusive dressings on treated areas

---

If HPA axis suppression test is abnormal at the End of Treatment Visit, subjects should be advised to avoid products containing corticosteroids until recovery is determined.

## **7 STUDY PROCEDURES AND EVALUATIONS**

### **7.1 Informed Consent Process**

Informed consent must be obtained from the subject's legal guardian before a subject can participate in the study, prior to performing any study related procedures and before withdrawal of any therapies prohibited during the study. The investigator must discuss the study fully with the subject and the legal guardian. Subjects must demonstrate their willingness to participate in the study and comply with the study procedures by giving written assent. The consent form must be signed and dated by the subject's legal guardian. A copy of the consent form and assent form must be given to the legal guardian and subject, and the date of the consent process and who conducted the consent process must be documented in the source documents.

### **7.2 Screening**

The Screening Visit should occur no more than 60 days before the Baseline Visit.

The screening ACTH stimulation test must be conducted at least 14 days and no more than 28 days prior to the Baseline Visit. Subjects should tentatively qualify for study enrollment before the ACTH stimulation test is conducted. The ACTH stimulation test can be conducted on the day of the Screening Visit (if timing is appropriate) or on a separate day (e.g., when washout is needed).

The subject's medical history should be recorded in the source documents and reviewed for study eligibility. However, only the concurrent medical conditions need to be entered on the CRF.

A screen failure is a subject who received information about the study, including signing an assent/consent form, and possibly performing some study related procedures but was not randomized. The subject number, date of visit, date of consent, reason for screen failure, and study status (screen failure) will be captured on the CRF for every screen failure subject.

### **7.3 Demographic and Baseline Characteristics**

Demographic variables include age (computed from date of birth and Baseline Visit date), race, ethnicity, weight and sex. Baseline characteristics are the baseline values for ACTH stimulation test, IGA and BSA affected (body surface area affected excluding the face, scalp, groin, axillae and other intertriginous areas). BSA should be determined using the area of the subject's hand print (palm plus extended fingers) as an estimate of 1% BSA ([Finlay, 2005](#)).

### **7.4 Efficacy Assessments**

#### **7.4.1 Investigator's Global Assessment (IGA)**

Clinical determinations of disease severity using IGA will be performed at each visit from screening through the end of treatment. The IGA scoring is shown in [Table 2](#) below. IGA score

is a static assessment of disease severity and should be based on overall severity of signs at the visit. The inclusion criteria for this study require a Baseline IGA of at least 3 (moderate).

**Table 2: Investigator's Global Assessment (IGA) of Disease Severity**

Score	Grade	Definition
0	None	No plaque elevation above normal skin level may have residual non-erythematous discoloredation no psoriatic scale no erythema
1	Minimal or Almost clear	No more than: very slight elevation above normal skin level faint light pink coloration occasional very fine scale partially covering some of the lesions
2	Mild	No more than: slight but definite elevation of plaque above normal skin level light red coloration fine scale with some lesions partially covered
3	Moderate	No more than: definite elevation with rounded or sloped edges to plaque definite red coloration somewhat coarse scale with most lesions partially covered
4	Severe/ Very Severe	At least one: marked elevation with hard, sharp edges to plaque dark red coloration coarse, thick scale with virtually all lesions mostly covered and a rough surface

#### 7.4.2 BSA

BSA affected should be determined at the Screening, Baseline and End of Treatment Visits. BSA should be determined using the area of the subject's hand print (palm plus extended fingers) as an estimate of 1% BSA ([Finlay, 2005](#)).

### 7.5 Safety Assessments

#### 7.5.1 ACTH Stimulation Test

Subjects will be tested for HPA axis function using the ACTH stimulation test (cosyntropin i.v. or i.m. injection) at a Screening Visit and at the End of Treatment Visit. If HPA axis is suppressed at the end of treatment, another test will be administered 28 days later (at approximately Day 43 or 57, as appropriate) to confirm recovery. The ACTH stimulation test will be repeated approximately every 28 days until recovery is confirmed or until the cause of suppression is diagnosed. The test should be conducted between the hours of 7:00 and 9:30 AM. The Screening Visit test must be normal to be eligible for the study (cortisol level > 18 ug/dL at 30 minutes post stimulation). The End of Treatment test should be performed within 1 hour of the time when the Screening Visit test was performed.

For female subjects, a urine pregnancy test will be conducted *just prior* to the ACTH stimulation test. The test must have a sensitivity of at least 25 mIU/mL for human chorionic gonadotropin. The test must be negative to be eligible for the study.

**Procedure**

The entire test must be completed between approximately 7:00 am and 9:30 am, including pre- and post-stimulation blood and saliva samples. A pre-dose, control blood sample of 4 to 5 mL will be collected in a serum separator tube and a pre-dose, control saliva sample of 0.2 mL to 0.5 mL will be collected with a Salivette® collection system. Then 0.25 mg of cosyntropin, reconstituted according to package insert instructions, will be injected intravenously or intramuscularly. The chosen route should be recorded on the CRF. The reconstituted drug product should be inspected visually for particulate matter and discoloration prior to injection. Reconstituted cosyntropin should not be retained. A second blood sample of 4 to 5 mL and a second saliva sample of 0.2 mL to 0.5 mL will be collected 30 minutes after injection of cosyntropin. Both blood sampling and cosyntropin administration (if administered intravenously) should take place in the same arm, if possible.

**Sample Preparation and Shipment**

All blood samples for estimation of serum cortisol levels should be centrifuged, serum separated and stored frozen (-20° C) until shipped according to the laboratory manual. Saliva samples should be stored frozen (-20° C) until shipped according to the laboratory manual.

**Sample Analysis**

The determination of the serum and saliva cortisol levels will be estimated by a validated method. A normal response is defined as a serum cortisol level of more than 18 ug/dL at 30 minutes post-stimulation. An abnormal response at end of treatment should be recorded as an adverse event of HPA axis suppression.

**7.5.2 Other Safety Assessments**

Other safety assessments include vital signs, local cutaneous safety evaluation of the treated skin, and adverse events (AEs). Vital signs (blood pressure, pulse) will be collected at each visit. Adverse events will be collected by spontaneous reports from subjects and legal guardian, either verbal or recorded in the subject diary, by directed questioning of subjects and legal guardian, and by observation (see [Section 8](#) for details about AEs).

At Visits 2 (Baseline) through the End of Treatment Visit, the investigator will assess local cutaneous safety by examining treated areas for clinically significant atrophy and telangiectasia that will be recorded on the CRF as present or absent. The investigator will also ask the subject if any burning/stinging, pain, or itching has occurred in the treated areas since the last visit (for Visit 2 in the last 2 weeks). Baseline assessments are made prior to first application.

Subsequent to the Baseline Visit, for each symptom reported by subjects and/or each clinically significant sign, the presence of the sign or symptom must be recorded as “Yes” even if severity is not worse than Baseline. An adverse event should be recorded if the severity is worse than Baseline.

For female subjects, urine pregnancy tests will be conducted at Screening, Baseline, and every subsequent visit. These tests will be conducted just prior to the ACTH stimulation test, as

---

appropriate. The test must have a sensitivity of at least 25 mIU/mL for human chorionic gonadotropin.

Adverse events, whether believed by the investigator to be related or unrelated to treatment, will be recorded on the CRF.

### **7.5.3 Drug Concentration Measurements/PK Blood Sampling**

#### **Sampling Schedule**

A screening PK blood sample will be taken at the time of the screening ACTH stimulation test to obtain a baseline value.

At the End of Treatment Visit, subjects will apply the last dose of study product at the clinic up to 60 minutes after a pre-treatment PK blood sample is taken (0 hour – End of Treatment Visit). PK blood samples will then be collected at 1, 3 and 6 hours ( $\pm$  5 minutes) after application of the study product.

Each blood draw will be accomplished by a fresh, clean venipuncture or collection from previously implanted catheter. Blood (approximately 6 ml per PK time point) will be collected in NaF/Na2EDTA blood collection tubes. Approximately a total of 30 mL of blood per subject will be drawn for drug assays during the study (6 mL at the Screening Visit and 24 mL at the End of Treatment Visit).

#### **Sample Processing**

Within approximately 1 hour of collection, plasma should be separated and processed. Samples should be stored and shipped according to the laboratory manual.

#### **Analytical Procedure**

Plasma betamethasone, betamethasone-17-propionate, and betamethasone -17,21-dipropionate will be measured by a validated, LC/MS/MS analytical method with a limit of quantitation of at most 5 pg/mL. Each assay run should include standards and quality control samples. The reference standard should be obtained from an official source. Failed batches will be documented in a run summary.

A validation report describing the method accuracy, precision, linearity, and robustness must be available for the analytical procedure. Stability of analytes must be shown for the storage period before assay and during the assay procedures.

### **7.6 Early Withdrawal of Subjects**

1. Subjects should be withdrawn from the study if they or their legal guardian no longer wish to participate, are being uncooperative, or if the investigator feels that it is in the best interest of the subject to withdraw.
2. Subjects with protocol deviations or for whom it is discovered should have been excluded should not be withdrawn unless there is a safety concern. The protocol deviation should be recorded in the subject's chart and Sponsor Consultation form.

3. Subjects who experience an AE resulting in or requiring discontinuation of study product use should be encouraged, in conjunction with their legal guardian, to be followed until the AE is resolved or stabilized.
4. If a female subject becomes pregnant during the study, study product will be discontinued immediately and she will be followed through the pregnancy and delivery. Details of the pregnancy, delivery and health of the infant should be recorded on the Pregnancy Surveillance Form and the sponsor notified immediately.
5. At the time of study discontinuation, the investigator will record the reason for early withdrawal, date of last study product application, date of last visit or contact, collect adverse event data, and, if possible, perform all End of Treatment Visit specific evaluations. Every attempt should be made to contact subjects who are lost-to-follow-up via their legal guardian for a final safety assessment. At least three attempts must be documented in the subject's chart including the use of at least 1 certified letter. Any contact, either direct or indirect, should be made with the purpose to document the final status of the subject with regard to safety.
6. Subjects who withdraw early will not be replaced.

### **7.7 Modification of Protocol**

No amendments to this protocol can be made without consultation with and agreement of the sponsor, the FDA, and IRB. Amendments must be made in writing. Modifications needed for the safety of subjects will be made immediately with notifications made as soon as possible.

### **7.8 Early Termination of Study**

If it is determined by the sponsor or investigators that the study presents an unreasonable and significant risk to subjects, the study will be terminated as soon as possible, and in no event later than 5 working days following the determination that the study should be discontinued. The IRB and FDA must be notified as soon as possible about early termination of the study due to safety concerns.

### **7.9 Study Schedule**

Study Schedule charts can be found on pages [7](#) and [8](#). There are at least 4 or 5 study visits; Screening (Visit 1), Baseline (Visit 2, Day 1), Day 8 (Visit 3), Day 15 (Visit 4 – End of Treatment Visit for the 15-day treatment group), and Day 29 (Visit 5 – End of Treatment Visit for the 29-day treatment group). A supplemental Visit 5 or 6 (Day 43 or 57) may be required to repeat the ACTH stimulation test if it was abnormal at the End of Treatment Visit.

This is a short trial and it is imperative that subjects and their legal guardians understand the importance of attending each visit as scheduled. This should be discussed with the subject and legal guardian before randomization at Visit 2. Randomized subjects and legal guardians must be counseled to keep all scheduled appointments and to return to the site within the permitted visit windows for each treatment visit ( $\pm$  3 days for Visits). If a subject misses a visit, they and their legal guardians, should be encouraged to attend the next visit scheduled from the Baseline

---

Visit (Visit 2) date. It is especially important for the subject to complete the End of Treatment evaluation.

### **7.9.1 Visit 1 - Screening Visit (60 days or less from Baseline Visit 2)**

1. Obtain written informed consent from legal guardian and written assent from subject prior to completing any study procedures. Document informed consent and assent in the subject's study record.
2. List subject on Screening/Enrollment Log. Assign subject number consisting of the 3 digit site number followed by sequential 3 digit numbers starting with 001 (e.g. 400001, 400002, 400003, etc.).
3. Collect demographic data – date of birth, sex, race, weight, and ethnicity.
4. Review and record medical history and concomitant medications, therapies and procedures. Medical history should be collected for the prior 1 year period and concomitant medications, therapies and procedures collected from the prior 2 month period. (record on source only)
5. Screen subject according to the study inclusion/exclusion criteria to determine tentative eligibility.
6. Initiate any protocol required washout.
7. Assess severity of psoriasis using IGA (record on source only).
8. Assess BSA excluding face, scalp, axillae, groin and other intertriginous areas. (record on source only)
9. Collect vital signs (blood pressure, pulse). (record on source only)
10. Conduct urine pregnancy test (UPT) for all female subjects (record on source only). Test must be negative to proceed.
11. If tentatively eligible and UPT is negative, conduct ACTH stimulation test (approximately 10 mL of blood is required). This test should be conducted at least 14 days and no more than 28 days prior to Visit 2 (Baseline). The entire test, including pre- and post-stimulation blood and saliva samples, should be completed between approximately 7:00 am and 9:30 am. Schedule for another day if needed. Also a screening PK blood sample will be drawn to obtain a baseline value. Blood (approximately 6 ml) will be collected in NaF/Na2EDTA blood collection tubes for PK analysis.

**Note:** Subjects with an abnormal ACTH stimulation test (cortisol level  $\leq$  18 ug/dL at 30 minutes post stimulation) should be referred to their primary care physician, as needed.

### **7.9.2 Visit 2 - Day 1 - Baseline Visit**

1. Update the medical history and concomitant medications. Any medical event (not related to a protocol intervention) that occurred since informed consent was signed should be recorded as medical history if still ongoing.
2. Collect adverse events. Any new medical event, need for new medication, or change in medication dosing caused by a protocol procedure performed at the Screening Visit should

be considered an adverse event except for worsening of psoriasis.

3. Confirm eligibility according to inclusion/exclusion criteria.
4. Conduct urine pregnancy test on female subjects. Record method of contraception, as applicable, on source only.
5. Collect vital signs (blood pressure, pulse).
6. Conduct clinical assessments:
  - a. IGA ([Table 2](#))
  - b. Local cutaneous safety evaluation for clinically significant atrophy and telangiectasia in areas to be treated. The investigator should also ask the subject if any burning/stinging, pain, or itching has occurred in the areas to be treated in the last 14 days.
  - c. Diagram affected areas to be treated (excluding face, scalp, axillae, groin and other intertriginous areas).
  - d. Determine BSA excluding face, scalp, axillae, groin and other intertriginous areas.
7. Randomize the subject by referring to the randomization schedule and dispense study product to the subject/legal guardian. The tear-off panel from the box is to be affixed to the source document. Make a note on source document regarding treatment duration.
8. Instruct subject and legal guardian on study product use. Review the appropriate Subject Instructions with subject (See [Appendix 2](#)). Using the diagram of affected areas, have the subject treat the affected areas under supervision after weighing the study product.
9. Dispense and review use of diary. Remind subject and legal guardian to record actual application dates and/or potential adverse events as well as any medication used in the diary and to bring diary to each visit.
10. Schedule next visit.
11. Complete CRF for all subjects including screen failures. Only enter concurrent medical conditions and concomitant medications on the CRF.

### 7.9.3 Visit 3 - Day 8 ± 3 days

1. Evaluate treatment and protocol compliance and record any deviations. This includes a review of the diary card for number of applications and missed applications.
2. Conduct clinical assessments:
  - a. IGA ([Table 2](#))
  - b. Local cutaneous safety evaluation for clinically significant atrophy and telangiectasia in the treated areas. The investigator should also ask the subject and legal guardian if any burning/stinging, pain, or itching has occurred in the treated areas since the last visit.
  - c. Update diagram of affected areas to be treated. Subjects should continue to treat areas that have cleared and any new areas that develop during the treatment period.
3. Collect vital signs (blood pressure, pulse).

4. Conduct urine pregnancy test for female subjects. Test must be negative to proceed.
5. Collect adverse event data. This includes a review of the diary card for potential AEs.
6. Update concomitant medications data.
7. Redispense diary and review instructions and diagram of affected areas to be treated with subject.
8. If subject requires more study product, weigh then dispense the assigned study product, as needed. Collect and record weight of empty or nearly empty bottles. Re-dispense partially filled bottles.
9. Schedule next visit. Remind the subject to come to the next visit well hydrated.
10. Complete CRF.

#### **7.9.4 Visit 4 - Day 15 ± 3 days (29-day treatment group only; not applicable for 15-day treatment group)**

1. Evaluate treatment and protocol compliance and record any deviations. This includes a review of the diary card for number of applications and missed applications.
2. Conduct clinical assessments:
  - a. IGA ([Table 2](#))
  - b. Local cutaneous safety evaluation for clinically significant atrophy and telangiectasia in the treated areas. The investigator should also ask the subject and legal guardian if any burning/stinging, pain, or itching has occurred in the treated areas since the last visit.
  - c. Update diagram of affected areas to be treated. Subjects should continue to treat areas that have cleared.
3. Collect vital signs (blood pressure, pulse).
4. Collect adverse event data. This includes a review of the diary card for potential AEs.
5. Update concomitant medications data.
6. Conduct a urine pregnancy test for female subjects. The test must be negative for the subject to continue in the study.
7. Redispense diary and review instructions and diagram of affected areas to be treated with subject.
8. If subject requires more study product, weigh then dispense assigned study product, as needed. Collect and record weight of empty or nearly empty bottles. Re-dispense partially filled bottles.
9. Schedule next visit. Remind subject to come to the next visit well hydrated.
10. Complete CRF.

**7.9.5 Visit 4 (Day 15 ± 3 days) for 15-day treatment group or Visit 5 (Day 29 ± 3 days) for 29-day treatment group (End of Treatment Visit 7:00 am to 9:30 am)**

1. Evaluate treatment and protocol compliance and record any deviations. This includes a review of the diary card for number of applications and missed applications.
2. Conduct clinical assessments:
  - a. IGA ([Table 2](#))
  - b. Local cutaneous safety evaluation for clinically significant atrophy and telangiectasia in the treated areas. The investigator should also ask the subject if any burning/stinging, pain, or itching has occurred in the treated areas since the last visit.
  - c. Assess BSA excluding face, scalp, axillae, groin and other intertriginous areas.
3. Collect vital signs (blood pressure, pulse).
4. Collect adverse event data. This includes a review of the diary card for potential AEs.
5. Update concomitant medications data.
6. Conduct urine pregnancy test for female subjects. Test must be negative to proceed with the ACTH stimulation test.
7. Draw pre-treatment (0 hour) PK blood sample no more than 60 minutes before planned study product application and process sample. Blood (approximately 6 ml) will be collected in NaF/Na2EDTA blood collection tubes.
8. Collect all study product bottles and record weight.
9. Supervise last application of study product by subject. Record weight of bottle after application.
10. Draw post-treatment PK blood samples at 1, 3 and 6 hours after study product application and process samples. Blood (approximately 6 ml each sample for a total of 18 mL) will be collected in NaF/Na2EDTA blood collection tubes.
11. Conduct ACTH stimulation test after the last application (approximately 5 mL for each sample for a total of 10 mL). The entire test, including pre- and post-stimulation blood and saliva samples, should be completed between approximately 7:00 am and 9:30 am and within one hour of the time of the screening ACTH stimulation test.
12. Collect study diary.
13. Complete CRF.

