### **8.1 Adverse Event Reporting Period**

Adverse event data must be collected from the time treatment is initiated until study product treatment is discontinued except for spontaneously reported serious adverse events which should be reported up to 30 days after discontinuing study product use and entered on the CRF. Adverse events occurring from the time of the Screening Visit until the Baseline Visit associated with study procedures should also be reported for all subjects including screen failures. Abnormal screening ACTH stimulation test should not be reported as an adverse event. Abnormal End of Treatment ACTH stimulation tests will be recorded as adverse events of HPA axis suppression related to study product and will be repeated until HPA axis is stabilized (or explained).

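### At the End of Treatment Visit no adverse event or local skin question is scheduled after the last application and the cosyntropin test, and Section 8.1 closes non-serious collection when product stops

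*Combined protocol and SAP*

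**What the plan says.** **Section 7.9.5, End of Treatment Visit, in listed order:**

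- Step 2b, local skin evaluation, which looks back: "The investigator should also ask the subject if any burning/stinging, pain, or itching has occurred in the treated areas since the last visit".
- Step 4, adverse events: "Collect adverse event data. This includes a review of the diary card for potential AEs". The same sentence stands in 7.9.3 and 7.9.4; this point concerns its place in 7.9.5.
- Step 9: "Supervise last application of study product by subject. Record weight of bottle after application".
- Step 10: "Draw post-treatment PK blood samples at 1, 3 and 6 hours after study product application and process samples".
- Step 11: "Conduct ACTH stimulation test after the last application", to be finished by about 9:30 am.
- Steps 12 and 13 collect the diary and complete the CRF.

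**Section 8.1, reporting period.** Adverse event data are collected from the start of treatment "until study product treatment is discontinued". Serious events reported spontaneously are taken for 30 days more, and an abnormal End of Treatment ACTH result is itself recorded as an adverse event. Procedure-related events between Screening and Baseline are also reportable. No matching sentence covers procedures at End of Treatment.

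**Elsewhere.** Sections 7.5.2 and 8 collect events by spontaneous report, directed questioning and observation. Both visit schedules limit the Day 43 or Day 57 visit to subjects with an abnormal End of Treatment test. In Section 7.9.6 the adverse event step (4) follows the ACTH test (3). Section 11.5.5 gives treatment-emergent events a start date but no end.

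**The concern.** At every other treatment visit the order of steps does no harm. The first supervised application at Baseline, for example, comes after that visit's adverse event step, but the Day 8 visit asks about the interval. End of Treatment has no such backstop unless the ACTH test is abnormal.

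The protocol treats the reactions in question as relevant. It excludes subjects with a previous adverse reaction to cosyntropin, makes events caused by screening procedures reportable, and puts burning and itching at the head of its list of local reactions to topical corticosteroids. Yet the second cosyntropin injection and the last dose are followed by no directed question.

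Section 8.1 adds uncertainty. Read literally, its period closes at the last application, before the test. Adverse event steps nevertheless exist at Day 43 and Day 57, and the treatment-emergent definition stays open. A site could reasonably disagree with another on whether a mild reaction later on the last morning is reportable. What is at stake is the completeness and consistency of non-serious safety data in a study whose purpose is safety.

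**Working it through.** The plan states no figure that can be reproduced here; Section 11.1 gives no statistical justification for the sample size. The check compares the texts and then estimates how many subjects are affected.

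**1. Order.** Steps 2b and 4 are listed before steps 9 and 11. Steps 7 to 13 contain neither an adverse event question nor a local skin question.

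**2. Is the list a clock?** Not strictly. Assume, from the visit heading, that the application is no earlier than 7:00. The 6-hour draw in step 10 is then at 7:00 + 6 h = 13:00 or later, yet step 11 must end by about 9:30. So step 11 has to be done while step 10 is still running. Steps 9 and 11 are nevertheless fixed relative to each other, because the test is explicitly placed after the application. The subject is still due for a blood draw at least 13:00 − 9:30 = 3.5 hours after the test window closes. Observation is possible in that time, but no inquiry is instructed.

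**3. Share of exposure.** With two applications a day and one on the last day, the nominal count is 2 × (D − 1) + 1:

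- 15-day arm: 2 × 14 + 1 = 29, so the last application is 1/29 = 3.4%.
- 29-day arm: 2 × 28 + 1 = 57, so it is 1/57 = 1.8%.

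For cosyntropin, the End of Treatment injection is one of the two planned for every subject.

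**4. Subjects with no later scheduled inquiry.** Inputs are 25 subjects per arm (Section 11.1) and the adult suppression rates of 5/24 at Day 15 and 0/24 at Day 29 (Section 1). Assume that these rates carry over to adolescents and that all 50 subjects are tested.

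| Arm | Expected to return | Exact 95% limits for the rate | Limits × 25 |
|---|---|---|---|
| 15-day | 25 × 5/24 = 5.2 | 7.1% to 42.2% | 1.8 to 10.5 |
| 29-day | 25 × 0/24 = 0 | 0% to 14.2% | 0 to 3.6 |

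- Central estimate: 50 − 5.2 − 0 = 44.8, about 45 of 50 (90%).
- Low end: 50 − 10.5 − 3.6 = 35.9, about 36.
- High end: 50 − 1.8 − 0 = 48.2, about 48.

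The range takes both arms at the same extreme, so it is wider than a joint 95% interval. Subjects who do return are next asked about 28 days later (43 − 15, or 57 − 29).

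**5. Section 8.1 against the rest.**

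| Place | What it implies about the end of collection |
|---|---|
| 8.1 | Product discontinuation, with the serious-event and abnormal-ACTH provisions |
| 7.9.6 and both schedules | Collection at Day 43 or Day 57 in those who return |
| 11.5.5 | Treatment-emergent, no end |

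These three do not agree.

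**The case against.** The strongest reply is that nothing forbids capture. Spontaneous report and observation remain open, the definition in Section 8 covers events related to trial procedures, and Section 8.2 has the investigator record every event. Subjects are due at the site for hours after the test. Events carry a start date, not a clock time, so a reaction later that morning shares its date with the last dose and need not fall outside the period in Section 8.1. Section 8.1 itself accepts one finding from after the last dose, the abnormal ACTH result. The schedules assign adverse event assessment to the visit as a whole, and step numbers do not fix its time.

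Most of this stands, and it rules out three stronger readings that a reader might infer.

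- **That reactions to the last dose and the test are not captured, or that half of all cosyntropin injections fall outside collection.** The routes above and the 30-day provision for serious events contradict this. What is missing is a scheduled question.
- **That a number of missed events can be stated.** The documents give no rate of reaction to cosyntropin or to a single application, so any count would rest on an assumed rate and on zero capture by the other routes.
- **That events in screen failures cannot be recorded.** Section 7.2 lists items ending with "reason for screen failure, and study status (screen failure) will be captured on the CRF for every screen failure subject" and names no event field. That list is not said to be exhaustive, and the CRF is not among the documents. Section 8.1 requires events "associated with study procedures should also be reported for all subjects including screen failures", and Section 7.9.2 calls for a CRF for screen failures.

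The reply does not remove the core. Loose ordering and day-level dating make capture possible, but they do not put a question after the last dose or the injection. The conflict between Section 8.1 and the retest visits remains under either reading.

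**Conclusion.** The point holds in a limited form. After the last supervised application and the End of Treatment cosyntropin test, no adverse event or local skin inquiry is scheduled for subjects with a normal test. Section 8.1, read literally, has closed non-serious collection by then. Non-serious reactions may therefore be under-recorded, to an extent that the documents do not allow to be estimated.

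The number of subjects affected rests on the adult rates carrying over and on full attendance. Reliance on the adult rates is weak, since they come from 24 subjects per arm in another age group, but the conclusion that most subjects are affected holds across the whole range. For the product itself the gap is small, one application in 29 or 57. It is larger for the test injection, one of two. The primary variable, the proportion with an abnormal cortisol response, is not touched. The change is worth making because it costs little and the study's purpose is safety.

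**What to change.** **Section 7.9.5.** Add a step after the 6-hour PK sample, or move step 4 there, to ask about adverse events and repeat the local tolerability questions for the last application. Record these answers separately from the step 2b assessment, which covers the interval since the previous visit, so that the by-visit summary in Section 11.5.2 keeps one meaning.

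**Section 8.1.** Let collection run through completion of the End of Treatment procedures and, for subjects who return, through the Day 43 or Day 57 visit and any repeat ACTH visits. Ending it at the End of Treatment procedures alone would still conflict with Section 7.9.6 and the schedules. State the same end point in the treatment-emergent definition in Section 11.5.5.

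**Cost.** One more question and one CRF line per subject, at a time when the subject is already due for a blood draw. Adverse event counts may rise slightly. Under Section 11.5.5 a reaction to the End of Treatment test would count as treatment-emergent, and the causality categories in Section 8.3.2 can mark it as unrelated to study product where that is the investigator's judgement.
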